CCGs and commissioning: In two meetings with [name], the principal commissioner of children's services and CCG GP leads there was clear support for the proposed study to inform implementation of the NICE guideline into Leicestershire GP practices. This was identified as a priority funding area for discussion in the next financial year.

Leicestershire Partnership Trust Respiratory Specialist Nurse Lead: The implementation study was discussed with [name], lead respiratory nurse in the Leicestershire Partnership Trust (LPT). The LPT respiratory nurse team helped implement and continues to support the implementation of spirometry testing for patients with COPD in Leicestershire primary care practices. [name] experience with implementation informed the study protocol and advised on how best to start addressing the training needs and barriers to implementation and joined the study team.

The current training package is usually delivered to individual PN/HCAs during a 2-hour training session preceding a joint COPD clinic and consists of a PowerPoint presentation on performance and interpretation of spirometry followed by hands on training. Depending on the level of experience of the PN/HCA the spirometry testing of patients in the clinic will be either supervised or supported where necessary or, where the PN/HCA is naïve to spirometry, she/he will observe at least 10 patients before performing supervised spirometry. Nurses are referred to 'A Guide to Performing Quality Assured Diagnostic Spirometry' (13) for further information on spirometry testing. The guide is supported by the NHS, Asthma UK, Primary Care Respiratory Society UK, BTS, the Association for Respiratory Technology & Physiology and others but its emphasis is on the testing in adults with COPD. Additionally, in order to obtain LPT accreditation the PN/HCA has to send in 10 spirometry tracings of which 8 have to comply with Association for Respiratory Technology & Physiology standards and be correctly interpreted. Group sessions for several practices located in close proximity are offered up to four times per year and one to one sessions are offered as appropriate with GPs who interpret the spirometry.

Rationale

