6. STUDY DESIGN SUMMARY

6.1 Summary of Trial Design

This study will employ both qualitative and quantitative measures in order to evaluate the resources required to implement routine lung function testing for children in primary care; and to investigate the impact this would have on diagnosis in children with suspected or presumed asthma. In total we hope to recruit between 3-6 GP sites across Leicestershire and Northamptonshire for the study, which would represent a patient population of ~120,000-150,000 people, representing 1500-2000 children potentially eligible to take part in the study based on our preliminary data. Primary care sites will be approached by the study team with assistance from the CCG R+D manager for Leicester ([name]) and the CRN locality manager for East Midlands ([name]). We aim to recruit sites of differing sizes and with different patient demographics.

Site survey questionnaires will be completed for each site by the study team to gather information about the individual practice's patient population and current asthma review set up. Readiness for change questionnaires will be used to investigate staff opinions, concerns and perceived barriers to implementation. These will be sent out to GPs, practice nurses, HCAs and practice managers at each participating site. The study team will develop and refine a package of training and support which will be based on an existing training programme for primary care practitioners to perform spirometry on adult patients with COPD in Leicestershire primary care practices. We will evaluate the success of the training by supporting and monitoring the primary care practitioners utilising these tests in primary care asthma review clinics. The length of training required in order for different staff groups to be able to perform spirometry and FeNO testing independently will be documented.

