6.2 Primary and Secondary Endpoints

The primary end point to this study will be when designated healthcare staff at each participating GP practice are able to independently and competently perform and interpret objective lung function tests; and have done so on all the children with suspected/presumed asthma on their patient register who have agreed to attend an asthma review clinic.

The secondary endpoint is when we have developed and refined a training and support package for primary care staff in the use of spirometry and FeNO testing in children; that is both acceptable to end-users and sustainable by the team delivering the training.

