Participants will be shown how to interpret the data first by examining the graphical recordings, ('pattern recognition'), and then by comparing measured outputs (FEV1, FVC, and FEV1/FVC) with predicted values appropriate for the sex, age and height of the child. This approach aims to identify any individual who may have a condition other than asthma (e.g. fixed obstruction), and then quantify the extent of any deficit in lung function. Where measurements are available before and after a bronchodilator the extent of any change in lung function is a measure of bronchial responsiveness.

In addition to training in spirometry, participants will be trained in the performance and interpretation of exhaled nitric oxide testing in children. While this requires careful instructions to be provided to the child so that s/he exhales steadily into the machine, there is minimal requirement for training in interpretation, since this is a straightforward single-number output.

We will also discuss asthma control tests, asthma action plans and inhaler technique but we are aware that many PN/HCAs will be familiar with asthma action plans and the checking of inhaler technique already. PN/HCAs will be able to retain copies of the teaching materials for private learning or revision, and are encouraged to contact the implementation team at any time if they have questions or want further training.

We will supervise the PN/HCAs performing at least 10 paediatric lung function tests or until they are assessed as competent by both the study team and themselves. This will be continually assessed and feed-back given to the PN/HCA. This approach has been employed successfully by the Respiratory Specialist Nurse Team for the Leicestershire Partnership NHS Trust. We will also point nurses towards accredited courses for further training.

A virtually-delivered quality improvement programme designed to improve primary care management for children with asthma has shown increased spirometry quality and improved assessment of asthma severity levels (14).

Success of the intervention will be defined as every participating surgery having a team which can regularly and competently provide objective lung function tests to children 5-16 years old.

Capacity Requirements

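### Competence, the core of the primary endpoint, rests on a supervision rule with no tracing-quality standard, although the local training scheme that the protocol describes has one

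*Combined protocol and SAP*

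**What the plan says.** Section 6.2 makes it part of the primary endpoint that "designated healthcare staff at each participating GP practice are able to independently and competently perform and interpret objective lung function tests". A second part, on coverage, requires that they "have done so on all the children with suspected/presumed asthma on their patient register who have agreed to attend an asthma review clinic". Section 9.1 defines success of the intervention as "every participating surgery having a team which can regularly and competently provide objective lung function tests to children 5-16 years old". None of these defines 'competently'.

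The only rule in the document that comes near a definition is the supervision rule in 9.1: staff are supervised "performing at least 10 paediatric lung function tests or until they are assessed as competent by both the study team and themselves". The protocol adds that assessment is continual and that feedback is given, but names no criterion. It then supports the rule by experience: "This approach has been employed successfully by the Respiratory Specialist Nurse Team for the Leicestershire Partnership NHS Trust".

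Section 4 describes that team's existing adult COPD programme. To gain its accreditation, "the PN/HCA has to send in 10 spirometry tracings of which 8 have to comply with" a named professional standard, and those tracings must also be correctly interpreted.

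Section 6.1 bases the study's training package on the existing programme and promises a result that depends on the same sign-off point: "The length of training required in order for different staff groups to be able to perform spirometry and FeNO testing independently will be documented".

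**The concern.** The primary objective is to evaluate what training and capacity practices need. A statement that a practice has reached competence, or that a staff group needed a given amount of training to become independent, carries information only if competence is fixed by something other than the completion of training or the opinion of those giving and receiving it. As written, no observable standard separates a trainee who produces acceptable, correctly interpreted tracings from one who does not.

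Three results depend on this: the competence part of the primary endpoint, the success statement for each surgery, and the length of training to independence. Tests done by staff after release also feed the secondary counts of confirmed diagnoses and misdiagnoses (5.2).

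**Working it through.** **Step 1. The two readings of 'or' in 9.1.**
- Literal: either condition ends supervision. Ten tests suffice whatever their quality, and joint agreement suffices after fewer than ten.
- Loose: 'at least 10' is a floor, and supervision continues until both parties are satisfied. Release then depends on a judgement with no stated criterion, made by the people who delivered the training together with the trainee.

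Neither reading requires a tracing to meet a standard.

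**Step 2. Is competence measured anywhere else?**
- 8.3 applies ATS/ERS standards to each child's manoeuvre, but records best effort when repeatability is not reached. It does not link this to staff sign-off.
- 9.1 lists recognising technically acceptable data, and recognising a child who cannot do the test, as training content, not as a pass mark.
- 4 gives the 8-of-10 mark, but as a feature of the existing adult scheme. The protocol does not say that it applies here.
- 11 contains no analysis of competence or tracing quality.
- 8.3 and 15 store the traces, but no grading or over-reading is planned.

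**Step 3. What an objective mark would do.** The plan gives no figure to reproduce. Let p be the share of a trainee's tracings that are acceptable and correctly interpreted. The documents give no value for p, so a range is assumed, with tracings treated as independent. For one block of ten:

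P(pass) = P(X ≥ 8), X ~ Binomial(10, p) = 45p⁸(1−p)² + 10p⁹(1−p) + p¹⁰

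At p = 0.5: 45/1024 + 10/1024 + 1/1024 = 56/1024 = 0.0547.

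If a fresh, non-overlapping block follows each failure, the chance of having passed by block k is 1 − (1 − P)ᵏ. At p = 0.5 and k = 2: 1 − 0.9453² = 0.106.

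| True rate p | One block | By two blocks | By four blocks |
|---|---|---|---|
| 50% | 5.5% | 10.6% | 20.2% |
| 60% | 16.7% | 30.7% | 51.9% |
| 70% | 38.3% | 61.9% | 85.5% |
| 80% | 67.8% | 89.6% | 98.9% |
| 90% | 93.0% | 99.5% | >99.9% |

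**Step 4. Why fixed blocks.** If the mark were 8 of the latest 10, checked after every test, each new tracing would give another chance. By simulation under the same assumptions, a 50% trainee would pass by 20 tests about 20% of the time and by 40 tests about 42%. Fixed blocks over the same 20 and 40 tests give 10.6% and 20.2%.

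**Step 5. The current rule.** No such table can be made for 9.1 as written, because neither route out of supervision depends on p through a stated threshold.

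**The case against.** The strongest reply is that the text has been read too harshly. 'At least 10' sets a minimum, the next sentence promises continual assessment, 6.1 promises support and monitoring in clinics, and 9.1 offers further training on request. A natural reading is ten or more, until competent. This stands: a reader might infer that every trainee is released at ten tests regardless of skill, but that holds only on the literal reading. It does not supply a criterion for the judgement.

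Second, 6.2 does not cite the 9.1 rule and also has a coverage part. A reader might infer that the primary endpoint can be met in every practice whatever the skill of its staff. The documents do not say so: sign-off alone does not complete the endpoint, and the link from supervision to endpoint is an inference, made because no other competence measure is given. Coverage counts children tested, not the quality of tests.

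Third, a reader might infer that the study discarded a quality mark that its own model programme used. Section 4 presents accreditation as a step additional to training, in adults with COPD, and the approach that 9.1 calls successful is supervision with assessment. The protocol is silent on adopting the mark. It does not reject it.

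Fourth, a tracing mark mixes the child's ability with the staff member's skill, and 8.3 accepts that repeatability is hard for younger children. This stands and shapes the fix.

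Last, test timings and sessions needed do not depend on the wording of the sign-off rule. This also stands.

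**Conclusion.** The concern holds in a limited form. On either reading, 9.1 ends supervision without a tracing-quality standard, and nothing else in the document measures "able to independently and competently perform and interpret objective lung function tests". The competence part of the primary endpoint, the success definition and the length of training to independence therefore share an undefined point. This should be settled before results are interpreted.

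The size cannot be stated as a bias, because the documents give no acceptable-tracing rates and no number of staff per practice. The table shows only that an 8-of-10 mark on one block separates weak from strong trainees (5.5% at a true rate of 50% against 93.0% at 90%), under assumed rates and independence. Repeated blocks raise all these figures.

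Two stronger conclusions are not supported. With 3-6 practices, it is tempting to say that one or two wrongly signed-off staff would reverse the study's conclusion. Success is defined by each surgery's team and team sizes are not given, so this cannot be shown. Nor does the gap make the whole study uninformative, since the capacity results stand apart from it.

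**What to change.** In 9.1, replace 'or' with 'and', and add an objective mark. Supervision would end when the staff member has done at least 10 supervised paediatric tests, the study team and the trainee agree on competence, and a fixed block of 10 tracings meets the mark. One example, adapted from section 4, is at least 8 of 10 technically acceptable and correctly interpreted. If the mark is not met, a fresh, non-overlapping block is started.

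The text should also:
- state how best-effort tests, and children found unable to do spirometry, count towards a block;
- add a simple criterion for performing and interpreting FeNO, which spirometry tracings do not cover;
- have an existing study-team member read the traces on site, from consented children only, because record access is by consent (8.1) and identifiable data may not leave the practice (14.1);
- record the number of supervised tests at sign-off, and count staff not signed off by study end as not competent;
- report self-rated confidence separately, as a descriptive measure;
- use this definition for 'competently' in 6.2 and in the success definition.

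A reader separate from the trainer and blinded to the tester would be desirable but is not essential.

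The cost is protocol wording and 10 tracings to read per trainee per block, more for those who need a second block. The traces are already recorded and scanned, and the local respiratory nurse lead is already on the team. Because only consented children's traces can be read, a block may take more than ten tests to fill. Some staff will stay supervised longer, and stated success may be less favourable.

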8. STUDY PROCEDURES

8.1 Informed Consent

Children aged 5 to 16 years who fulfil the inclusion criteria will be identified from electronic searches performed by the practice staff for the purposes of inviting them for an asthma review. We will provide the practices with patient information sheets (PIS) to post out with the invitation letters sent out by the GPs themselves. The PIS will detail no less than: the exact nature of the study and that the parent is free to withdraw the participant from the study at any time for any reason without prejudice to future care, and that there is no obligation to give consent for access to their child's records in the first place. Even if the parent does not consent to the study, their child is still welcome to the full asthma review including lung function tests as these are part of recommended standard care.

On the day of the clinic, a member of the research team will talk to the family prior to their appointment and explain the study and to answer any questions. The participant will be allowed as much time as wished to consider the information, and the opportunity to question the study team to decide whether they will participate in the study.

It will be made clear that none of the tests performed in the asthma clinic, except the short health economic questionnaires, are part of the research and should be viewed as best practice. We are only seeking consent to: 1) access their child's electronic records in order to obtain information including recent exacerbations and medications prescribed, 2) record answers to a health economic questionnaires onto the CRF, 3) time how long it takes to perform each lung function test and 4) ask their GPs to contact them in 3-6 months' time by post to complete a follow up health economic questionnaire and ACT. Written consent will then be taken from the parents should they agree to participate.

The person who obtains the consent will be suitably qualified and experienced, and have been authorised to do so by the Chief Investigator as detailed on the Delegation of Authority and Signature log for the study. The original signed form will be retained at the study site within Investigator Site File (ISF). A copy of the signed Informed Consent will be given to participants and a copy retained in the participant medical notes. Anyone not medically qualified will undergo UHL consent training.

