8.8 Source Data

Source documents are original documents, data, and records from which participants' CRF data are obtained. These include, but are not limited to, GP electronic records (from which medical history and previous and concurrent medication may be summarised into the CRF) and hospital correspondence.

CRF entries will be considered source data if the CRF is the site of the original

recording (e.g., there is no other written or electronic record of data). In this study the CRF will be used as the source document for time taken to perform spirometry and FeNO and health economic questionnaire answers only.

All documents will be stored safely in confidential conditions. On all study-specific documents, other than the signed consent, the participant will be referred to by the study participant number/code, not by name.

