We will assess additional capacity needs by timing how long each lung function test takes to perform in addition to the routine asthma review at each surgery. We will also be able to evaluate the number of patients who can be reliably reviewed and tested per session, thus elucidating how many sessions a typical GP practice would have to support in order to provide regular lung function testing to children. This information would further inform the costs required to sustain new NICE recommended practice.

Health Economic Analysis

This will take the form of a questionnaire delivered to parents at the time of the asthma review and a further postal questionnaire 3-6 months following the review. Analysis of this data will be supported by a health economist.

Assessment of Impact of Implementation to Processes of Care

Following the initial review appointment, we will access the electronic records of consented participants. We will seek information on changes to prescribed asthma medications (bronchodilators, oral steroids and inhaled steroids), exacerbations since review, hospital admissions/attendances since review and whether their originally diagnoses had changed as a result of the availability of objective tests.

With parental consent, we will also send out a repeat ACT by post 3-6 months following the initial review.

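### Routine capacity is to be derived from every timed test, with no rule to separate tests done under supervision while staff are still learning

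*Combined protocol and SAP*

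**What the plan says.** The primary objective (section 5.1) has two parts: the training that practices need and the capacity that they need.

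**Capacity.** Section 9.1 states: "We will assess additional capacity needs by timing how long each lung function test takes to perform in addition to the routine asthma review". It adds the number of patients who can be reliably reviewed and tested per session, and from both it derives the sessions a typical practice would have to run and the cost of sustaining the service. Section 8.1 asks parents for consent to "time how long it takes to perform each lung function test". Section 8.8 says that "the CRF will be used as the source document for time taken to perform spirometry and FeNO", and names the health economic answers as the other such item.

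**Training.** Section 9.1 also states: "We will supervise the PN/HCAs performing at least 10 paediatric lung function tests or until they are assessed as competent", in the judgement of both the study team and the trainee. It continues: "This will be continually assessed and feed-back given to the PN/HCA". Section 6.1 evaluates the training by "supporting and monitoring the primary care practitioners utilising these tests in primary care asthma review clinics", and says that the length of training needed for independence will be documented by staff group.

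**Endpoint.** Section 6.2 requires that designated staff can test and interpret independently and competently, and "have done so on all the children with suspected/presumed asthma on their patient register" who agreed to attend. Section 9.1 defines success as every surgery having a team that can provide the tests regularly and competently.

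**The concern.** Routine capacity is a steady-state quantity. Training is a cost paid once per staff member. Section 4 says that practice staff usually have no experience of spirometry in children, so their first tests can be expected to be slower, with teaching and feedback during the test. If those tests are averaged with the rest, part of the training cost appears as recurring workload, and the two halves of the primary objective are no longer cleanly separated. The derived figures, patients per session and sessions per practice, carry the same mixture. The mixture also depends on how many staff each practice trains relative to its number of children, so practice-level times would differ for a reason unrelated to routine capacity.

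A second consequence concerns section 6.2. If the requirement to have tested all attending children carries the word independently with it, each child tested under supervision counts against the endpoint.

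**Working it through.** **Step 1: do supervised tests fall among the timed tests?** No passage says so outright, so the sections have to be read together.

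- Section 6.1 puts the training package before the record searches and invitations, which points to training being finished first.
- The taught session in 9.1 uses other people as test subjects and a bank of anonymised traces. It does not mention children. The supervised paediatric tests are a separate requirement.
- The only paediatric tests that the protocol describes are those in the review clinics. Section 6.1 places support and monitoring there, and section 17 has the research nurse organising joint clinics.
- Section 9.1 says that its approach is the one used by the Partnership Trust nurses. Section 4 describes that model as teaching followed by supervised testing of patients in a joint clinic.

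Overlap is the likely reading. Tests on children whose parents do not consent would not be timed, so some supervised tests may drop out.

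**Step 2: can they be separated later?** Sections 8.1 and 8.8 refer to test times. No section provides for operator, test order or supervised status alongside each time. Section 11.1 describes no analysis of test times.

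**Step 3: the plan's own figures.** Section 6.1 gives 1500-2000 eligible children and section 11.2 a recruitment rate of 50-70%. This gives 1500 x 0.50 = 750 up to 2000 x 0.70 = 1400. The planned 1000 lies inside the range and equals 2000 x 0.50. Section 17 funds 200 sessions; 3-4 a week for 60 weeks is 180-240, which contains 200. Then 1000 / 200 = 5 consented children per session. The documents give no test time, so there is no capacity figure to reproduce.

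**Step 4: share of supervised tests.** Inputs: 3-6 practices (section 6.1); 10 supervised tests per trainee (section 9.1); 1000 children. Assumptions: 1-3 trainees per practice, and one timed test per child.

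Share f = practices x trainees x 10 / 1000

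- Low: 3 x 1 x 10 / 1000 = 30 / 1000 = 3%
- Middle: 6 x 2 x 10 / 1000 = 120 / 1000 = 12%
- High: 6 x 3 x 10 / 1000 = 180 / 1000 = 18%

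If spirometry and FeNO count as separate tests, the denominator is about 2000 and the range halves to 1.5-9%. If trainees need 20 supervised tests, it doubles to 6-36%.

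**Step 5: effect on mean time.** Let k be supervised time divided by routine time (assumed 1.25-2). The combined mean is routine mean x [(1 - f) + f x k], so the overstatement is f x (k - 1).

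- f = 3%, k = 1.25: 0.03 x 0.25 = 0.75%, about 0.8%
- f = 12%, k = 1.5: 0.12 x 0.5 = 6%
- f = 18%, k = 2: 0.18 x 1 = 18%

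**Step 6: variation between practices.** With equal-sized practices (an assumption; section 6.1 seeks differing sizes), the share runs from 10 / 333 = 3% (three practices, one trainee) to 30 / 167 = 18% (six practices, three trainees).

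**Step 7: endpoint.** On the strict reading of section 6.2 and the assumptions of step 4, at most 100% - 18% = 82% to 100% - 3% = 97% of 1000 children could be tested independently. On the loose reading, where staff need only have performed and interpreted the tests, 100% is attainable.

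**The case against.** The strongest reply is that timing each test describes data collection, not analysis. No combined mean is specified anywhere, and the reference in 9.1 to patients who can be reliably tested per session fits steady-state throughput. This stands in part: combining the tests is what follows by default from a missing rule, and is not a stated plan. But the sessions figure is built on these times, and no passage restricts them.

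Three stronger readings are tempting.

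- *Learning tests cannot be separated afterwards.* The documents do not show this. Section 8.8 lists the items for which the CRF is the original source; it is not an inventory of CRF fields, and the CRF itself is not among the documents. Supervising at least 10 tests implies a count per trainee, and training length is to be documented. Such records might allow some separation. It is only not assured.
- *The primary endpoint cannot be met.* That rests on one reading of section 6.2. The other reading is attainable, and the success definition in 9.1 contains neither the independence condition nor the all-children condition. The defect is ambiguity.
- *The bias is large.* Trainee numbers and the time ratio are not in the documents, the denominator is uncertain, and the upper figures stack every high assumption. The capacity figure is also descriptive, with no test or decision threshold attached.

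**Conclusion.** The point holds as a cheap improvement. Followed as written, the plan lets supervised learning tests into a figure meant to describe regular testing at a typical practice, and the likely direction is overstatement. The size is unknown: about 0.8-18% of mean test time, given 1-3 trainees per practice, 10 supervised tests each, one timed test per child and a time ratio of 1.25-2. It would be about half that if spirometry and FeNO are counted separately, and negligible if few supervised tests are on consented children. Separately, section 6.2 and the success definition in 9.1 do not agree, and a practice could meet one and fail the other.

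**What to change.** 1. **CRF.** With each timed test, record the operator code with that operator's running test number, and supervised yes or no. The running number should count all the operator's paediatric tests, including those on children not in the study, so that it reflects experience.
2. **Section 9.1, Capacity Requirements.** Base time per test, patients per session and sessions per practice on tests done after sign-off, meaning the joint competence assessment already described there. For patients per session, use sessions in which every operator had been signed off. Report supervised test time separately, per trainee, as a training cost.
3. **Section 11.1.** Add a sentence describing this analysis, since test times are not mentioned there.
4. **Sections 6.2 and 9.1.** Make the endpoint and the success definition agree, for example by applying the all-children condition to children attending after sign-off and reporting supervised tests alongside. State also whether 10 supervised tests is a minimum or may be fewer if competence comes sooner.

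The cost is two short CRF fields, some rewording, and fewer tests in the routine estimate: 1000 - 180 = 820 to 1000 - 30 = 970 would remain under the assumptions above. The fields need to be in place before the clinics start.
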